## 2. Purpose of the study

a) Provide a brief lay summary of the project in <200 words. The lay summary should be readily understandable to the general public.

Our overall goal is to assess the feasibility and effectiveness of using text messages as an educational tool in order to improve health care utilization among the parents and caregivers of newborns; in particular, we seek to understand how educational text messages counteract the effects of low health literacy as it relates to non-urgent visits to the emergency department.

Page numbers from a sponsor's protocol/grant may be referenced in 2b and 2c.

b) List your research objectives (specific aims & hypotheses of the study).

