## Research Objectives

- 1) Evaluate the feasibility of sending educational text messages to the caregivers of newborns through 6 months of age.
- 2) Assess how text messaging affects urgent and non-urgent health care utilization across caregivers with varying levels of health literacy.

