## Hypotheses

- 1) Text messaging is a feasible and welcomed educational tool for caregivers of newborns.
- 2) Receiving educational text messages reduces the number of non-urgent visits to the ED for caregivers across all levels of health literacy.
- c) Describe the study design (e.g., single/double blind, parallel, crossover, control, experimental, observational, etc.). If the study is investigator-initiated, a timeline for individual subject recruitment, follow-up, and analysis for the study is required. Also, indicate if the subjects will be randomized.

We propose a prospective, randomized, single-blind experiment assessing the effectiveness of receiving educational text messages on health care utilization at caregivers of newborns across varying levels of health literacy.

All caregivers of newborns less than 2 months of age will be approached for enrollment during regular clinic visits to Danis Pediatrics in Cardinal Glennon Children's Medical Center. Enrollment will take place following their visit with a provider; we anticipate this process will take no more than 15 minutes. Subjects will receive educational text messages four times per week until the child is 6 months of age. The research team will conduct a review of the child's medical records until the child is one year old. We will enroll up to 260 participants, and we anticipate the study continuing for an additional 18 months - including time for analysis - beyond the date when the final subject is enrolled.

d) If subjects will be given placebo, please justify placebo use. \*Error! Hyperlink reference not valid.\*

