#### 3. Study Procedures

a) Yes No

No

Is this project a multicenter study (i.e., same project is conducted elsewhere by a different investigator) OR does this study involve conduct of research at multiple sites?

Is SLU acting as a coordinating center for other sites OR is the SLU PI a direct recipient of a federal grant for this research? If yes, complete and attach the Supplemental Application for Coordinating Center Activities.

Yes No

Will the SLU site be participating in all parts/procedures/arms of the study?

If No, explain what SLU will NOT participate in:

Page numbers from a sponsor's protocol/grant may be referenced in 3b, 3c, and 3d.

b) Describe all the procedures, from screening through end-of-study, that the human subject must undergo in the research project, including study visits, drug treatments, randomization and the procedures that are part of standard of care. Specify which procedures are for research and which are standard of care. Please note: The box below is for text only. If you would like to add tables, charts, etc., attach those files in the Attachment section (#16).

Any caregiver of a newborn, aged 0-2 months, that receives primary care at Danis Pediatrics, has reliable cellular and text messaging service, and speaks English will be approached for enrollment. If the caregiver is interested in receiving educational text messages about their new baby, they will meet with a member of the research team.

At enrollment, caregivers will complete a brief demographic survey and be given a researcher-administered health literacy test. We anticipate enrollment will take no longer than 15 minutes. Following enrollment, participants will be randomly assigned to either the group that receives only enhanced standard of care documents, or receives text messages in addition to enhanced standard of care documents.

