The primary outcome of 6-month ED use (no vs. yes) will be compared between study groups, Intervention vs. Control, using the chi-squared test of association. Other categorical outcome variables (e.g., keeping well child appointments, keeping immunization appointments) will also be analyzed this way. Multivariate analyses of dichotomous outcomes, including multiple logistic regression, will be conducted with Group as the independent variable and covariates like patient age, race, gender, etc., included as control variables. Time-to-event data (e.g., time to first ED visit after study entry) may be evaluated using a Cox proportional hazards regression model with Kaplan-Meier curves.

Because this study rests on the assumption that text messages are both delivered and read, this study has several validity checks in place. First, to assure messages are delivered, the company (TeleVox) that will service text messaging for this study provides daily reports regarding

message status. That is, we can see - within 24 hours - whether or not a message has been successfully sent to a subject. In this regard, we can then address any message failures with subjects by phone, or at subsequent visits. While we can track whether or not a message has been received, knowing if a message has been read or understood is a more difficult. We've included questions on our post-test that inquire about message use and subject involvement. These questions will serve as a statistical covariates in the analysis, such that the treatment effect would be stratified by the levels of self-reported use of and involvement with the texts.

- 8. Subject Population In the space below, please detail the participants that you are requesting to recruit (include description of each group requested)
- a) Expected age range of subjects. (For example ≥ 18 yrs to 90 yrs).

Subjects are likely between 15 and 65 years of age (age of caretakers including parents and guardians).

b) Number of evaluable subjects to be accrued at SLU or SLU site (this includes all sites under the direction of the SLU PI). up to 260

Exceeding the number listed here is a protocol violation. Prior IRB approval is required if additional participants are to be accrued. If applicable, this number should be consistent with your power analysis described in 3d.

c) Number of evaluable subjects to be accrued study wide. \*?HELP?\*

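### Hypothesis 2 is about the number of non-urgent ED visits, but section 3d states no analysis of that number; it also gives health literacy no stated role in the analysis

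*Protocol*

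**What the plan says.** **Aims.** The lay summary (section 2a) wants to learn "how educational text messages counteract the effects of low health literacy as it relates to non-urgent visits" to the ED. Objective 2 is wider: "Assess how text messaging affects urgent and non-urgent health care utilization across caregivers with varying levels of health literacy". Hypothesis 2 is the narrowest: "Receiving educational text messages reduces the number of non-urgent visits to the ED for caregivers across all levels of health literacy". The design statement in 2c also refers to varying literacy levels.

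**Data.** Under section 3b, caregivers will "be given a researcher-administered health literacy test" at enrollment, before random assignment. ED visits are to be classified by type and counted from the child's record up to one year of age. The Background reports 919 ED visits by 520 of the clinic's patients in half a year.

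**Analysis (section 3d).** "The primary outcome of 6-month ED use (no vs. yes) will be compared between study groups" by chi-squared test. Other categorical outcomes are handled the same way. Dichotomous outcomes also get multivariable models, including logistic regression, "with Group as the independent variable and covariates like patient age, race, gender, etc., included as control variables". Time to first ED visit may be analysed by Cox regression. In the paragraph on validity checks, "the treatment effect would be stratified by the levels of self-reported use of and involvement with the texts". Section 3d mentions neither literacy nor a count of visits.

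**The concern.** The main issue is the outcome. Any ED use combines urgent with non-urgent visits and scores one visit the same as five. The protocol's own data average 919/520 = 1.77 visits per attending child, so repeat visits are common. If texting mainly prevented second and third non-urgent visits, the primary test could miss it. If any ED use fell, the test could not say whether non-urgent visits were the reason. Followed as written, 3d does not test the quantity that Hypothesis 2 names.

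The smaller issue is literacy. The open-ended covariate list could take in the literacy score, but a control variable alone gives no effect by literacy level. The Background describes low literacy as sustaining non-urgent care seeking, so the baseline score is an obvious covariate as well as the dimension along which the aims are written. If the levels and the model form are not fixed before the data are seen, a literacy-specific result is weaker evidence.

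**Working it through.** **1. What the sample size covers.** Two-proportion formula with continuity correction, two-sided alpha 0.05, 80% power: 41% vs 20% gives 84 per group, 41% vs 25% gives 147, and 41% vs 23% gives 116. The protocol states 84, 147 and 115. The 115 is reproduced only if the stated 23% is read as the intervention-group rate. These figures size one overall comparison of any ED use; they size neither a visit count nor an effect by literacy level.

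**2. Hypothesis against stated analyses.**

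| Hypothesis 2 needs | Section 3d states |
|---|---|
| Number of visits | Yes/no outcomes, optional time to first visit |
| Non-urgent visits | Primary outcome is any ED use; no urgency split is named |
| Across literacy levels | Literacy named neither as covariate nor as reporting level |

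**3. Count analysis, whole group.** Control mean over six months: 0.41 × 919/520 = 0.725 visits. Negative binomial dispersion a is chosen so that 41% have at least one visit: (1 + 0.725a)^(-1/a) = 0.59, giving a = 1.14.

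The rate ratio (RR) must match the planned effect. At the same dispersion, 23% any use means (1 + 1.14m)^(-1/1.14) = 0.77, so m = 0.305 and RR = 0.305/0.725 = 0.42. The ratio of proportions, 23/41 = 0.56, is not that RR: in this model it corresponds to about 28% any use, a weaker effect.

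Assume that a share s of visits is non-urgent (not given; 30-80% used), with the same RR and dispersion for non-urgent visits. With mu = 0.725s,

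SE(log RR) = sqrt[(1/mu + a)/n + (1/(RR·mu) + a)/n], and power = Φ(|log RR|/SE − 1.96).

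Example: s = 0.5, n = 115, RR = 0.42: mu = 0.362, SE = 0.318, power 78%.

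| n per group | RR | s = 30% | s = 50% | s = 80% |
|---|---|---|---|---|
| 115 | 0.42 | 60% | 78% | 90% |
| 130 | 0.42 | 65% | 83% | 93% |
| 115 | 0.56 | 36% | 50% | 64% |
| 130 | 0.56 | 40% | 55% | 70% |

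The 130 per group is the enrollment cap ("We will enroll up to 260 participants") divided by two. At 115 per group and RR 0.42, the expected 95% CI runs from 0.19-0.91 (s = 30%) to 0.25-0.71 (s = 80%).

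**4. Any ED use within one literacy level.** Assume two levels, 41% vs 23% in each, and a share of 30-70% in the level considered (not given for this clinic). The variance term is v = 0.41×0.59 + 0.23×0.77 = 0.419, and the pooled rate is 0.32. With n per group in the level,

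half-width = 1.96·sqrt(v/n), and power = Φ[(0.18 − 1/n − 1.96·sqrt(2×0.32×0.68/n)) / sqrt(v/n)].

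Dropping the 1/n gives power without continuity correction.

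| Total per group | Share | n | CI half-width (points) | Power, corrected | Power, uncorrected |
|---|---|---|---|---|---|
| 115 | 30% | 34.5 | 21.6 | 27% | 36% |
| 115 | 50% | 57.5 | 16.7 | 46% | 54% |
| 115 | 70% | 80.5 | 14.1 | 63% | 69% |
| 130 | 30% | 39 | 20.3 | 31% | 40% |
| 130 | 50% | 65 | 15.7 | 52% | 60% |
| 130 | 70% | 91 | 13.3 | 69% | 74% |

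**The case against.** *Any ED use is a legitimate primary outcome.* This stands. Objective 2 covers urgent and non-urgent utilization, and 3d explains why the trial was sized on ED use. A reader might infer that the primary analysis misses the study's objective; the protocol does not support that. The mismatch is with Hypothesis 2.

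*The open wording may already cover non-urgent visits.* This stands in part. The clause on other categorical outcomes could take in any non-urgent visit, yes or no. It cannot take in the number of visits, and no other stated method does.

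*Subgroup detail belongs in an SAP.* This stands to a large extent for literacy, and it is why that point is the smaller one. An SAP that is not at hand may fix levels and model form, and literacy is declared in the aims and measured before assignment. One cannot say that literacy results would necessarily be chosen after the data are seen. Nor does the stratification by self-reported text use show that literacy was deliberately passed over: it belongs to a validity check on whether messages were read and is not a list of efficacy subgroups.

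*Hypothesis 2 may mean an overall effect in a population of mixed literacy.* This is a fair reading, and the overall comparison then needs no literacy split. The lay summary's aim of learning how texts offset low literacy would still have no stated analysis. The missing count analysis is unaffected by which reading is taken.

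*A count analysis would be underpowered.* A reader who takes 23/41 as the rate ratio might conclude this. That ratio implies about 28% any use, not the planned 23%; with the matching ratio of 0.42, power is reasonable over most of the range.

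**Conclusion.** The point holds and should be acted on, but it does not undermine the primary comparison. Hypothesis 2 names an outcome, the number of non-urgent ED visits, for which 3d states no analysis although the data will be collected. Literacy, which frames the aims, has no stated role in the analysis; this second part is weaker because an SAP may supply it and because the hypothesis can be read as an overall effect.

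Both parts rest on comparing the protocol's own sections and need no assumed figure. The sizes do rest on assumptions. Count-analysis power is 60-90% (115 per group) or 65-93% (130 per group) at a rate ratio of 0.42, and 36-64% or 40-70% at 0.56, for an assumed non-urgent share of 30-80%. The control mean combines the clinic's 41% incidence with the Background's visits per attender and is itself approximate. Within-level power is 27-63% or 31-69% with continuity correction, for an assumed literacy share of 30-70%. Estimates by literacy level can therefore describe, but will seldom confirm, an effect.

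**What to change.** Amend section 3d and leave the primary test as it is.

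1. Add a secondary whole-group count analysis of non-urgent ED visits, for example negative binomial. State its window, since the primary outcome is at six months while records are reviewed to one year. Fix the rule for calling a visit non-urgent before record review begins, and apply it without knowledge of group where feasible. Unblinding would not serve as the deadline, because the protocol says only that the study is single-blind and does not say that record reviewers are blinded.
2. Name the baseline literacy score as a covariate in the adjusted models.
3. Report the Group effect on 6-month ED use with 95% CIs at literacy levels fixed in advance (the test's own categories or named score percentiles). A Group-by-literacy term may be used to obtain them. Label these results exploratory, and state that a non-significant interaction will not be read as equal benefit.

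The cost is wording plus two analyses of data already planned. The classification rule, the count window and the literacy levels must be written down first. Enrollment and randomisation do not change. The downside is that literacy-specific estimates will be wide, and the count analysis may be inconclusive if the effect is weaker than planned or few visits are non-urgent.

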#### 1. Background

Page numbers from a sponsor's protocol/grant may be referenced in 1a and 1b.

 a) Provide an introduction and background information. Describe past experimental and/or clinical findings leading to the formulation of the study, if applicable. Investigator Initiated studies must cite references in the response provided or attach a bibliography. \*?HELP?\*

Health care utilization is a issue germane to health care providers, insurers, and patients alike. Reducing non-urgent visits to the emergency department (ED) and primary care providers can improve both the quality and cost of care. There are barriers, however, to educating patients about more appropriate health care utilization. Low health literacy is one such barrier, particularly for caregivers of pediatric patients. Research reveals that up to half of caregivers seeking treatment at the ED have low levels of health literacy; levels that can make it more difficult to not only make sound decisions, but also provide effective follow-up care. Moreover, low levels of literacy perpetuate a cycle of seeking care for non-urgent conditions. Education initiatives designed to counteract the effects of low health literacy on health care utilization have been shown to reduce non-urgent ED visits by as much as 80%. These education interventions, while effective, are complex, costly, or time-intensive. For example, home visits by a nurse, parenting classes, and video tools are all shown to reduce non-urgent ED use, but each poses a unique problem for implementation in high volume, urban, pediatric primary care clinic. To date, no study has examined the effectiveness of text messaging as a possible avenue for educating caregivers about issues related to health care utilization. Text messaging has been shown to support behavioral change, and represents a fast and cost-effective alternative to more labor-intensive and expensive alternatives.

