c) If the proposed study is a clinical trial where a drug, vaccine, device or other treatment is compared to a placebo group or comparison treatment group, what are the guidelines or endpoints by which early decisions regarding efficacy or lack of efficacy can be made? For example, it may be reasonable to stop enrollment on a study when efficacy has already been clearly demonstrated, to avoid unnecessary enrollments of additional subjects. Alternatively, it may be reasonable to stop enrollment when it is clear that efficacy will never be demonstrated, given the statistical power of the study as designed. Describe the guidelines that are in place to assist in making these determinations, if relevant to the proposed study.

NA

d) Describe how data analysis will be performed (statistical tests, methods of evaluating data) and indicate the smallest group/unit for which separate reporting will occur. For studies involving a questionnaire, if data and reliability information are available, please describe or provide references. For full board, unfunded studies describe sample size determination and power analysis. If none, please justify.

The sample size for the study was estimated to achieve 80% statistical power, assuming a non-directional test and a critical level for significance of alpha = .05, based on the primary outcome variable of emergency department (ED) use. The study was powered on the latter variable because it is expected to yield the smallest intervention effect. Danis Pediatric Center patients <13 months of age have a six-month incidence rate of presentation at the Cardinal Glennon Children's Hospital ED of 41% (clinic data). This rate was assumed as the baserate behavior for the Control group in the proposed research. Assuming an incidence rate in the Intervention group of 20-25% (difference from baserate behavior of 16-21%), sample sizes ranging from 84-147/group would yield adequate statistical power. Because this is a first-time study of this intervention in relation to ED use, a 23% effect size was targeted, requiring 115 subjects/group or 230 subjects total. Danis Pediatric Center encounters with study eligible patients average ~25 patients/week (conservative estimate); thus, with a 67% response rate (consistent with other research of this type in the Department of Pediatrics), the study will require 12-14 weeks to enroll this target number.

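### Health literacy is measured in every caregiver before assignment, but the fixed primary test is unadjusted and literacy is not a named covariate, so a modest, cheaply recoverable amount of precision is lost.

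*Protocol*

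**What the plan says.** Protocol section 3(b) sets the order of events. At enrolment, "caregivers will complete a brief demographic survey and be given a researcher-administered health literacy test". Assignment comes afterwards: "Following enrollment, participants will be randomly assigned". Nothing is said about stratification, blocking or minimisation.

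Section 3(d) fixes the primary analysis. Six-month ED use (no vs yes) is compared between the two groups "using the chi-squared test of association". Logistic regression is planned in addition, with Group as the independent variable and "covariates like patient age, race, gender, etc., included as control variables". The only other covariates described there are post-test answers about use of the texts, which are collected after randomisation.

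The Background gives the reason literacy matters to this trial: "low levels of literacy perpetuate a cycle of seeking care for non-urgent conditions". Objective 2 and Hypothesis 2 are also framed around levels of health literacy.

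**The concern.** The one baseline variable collected because of the trial's own theory has no stated part in the comparison that decides the trial. If literacy predicts ED use, two things follow. A chance difference between the arms in literacy shifts the estimated group difference in a way that could have been removed. And outcome variation that literacy explains stays in the standard error.

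There is also a question of credibility. If the arms turn out to differ on literacy and the score is then brought in under the open-ended list, the adjustment will look data-driven. Naming it beforehand avoids that dispute.

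This point concerns balance and precision of the overall comparison. It does not concern separate effects by literacy level.

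**Working it through.** **Inputs from the protocol, section 3(d).** The sample size was "estimated to achieve 80% statistical power", "assuming a non-directional test and a critical level for significance of alpha = .05". Control rate 41%; 115 per group, 230 in total; intervention rates considered 20-25%.

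**Assumed inputs.** Low-literacy share 50% (the Background says up to half, and of caregivers seeking ED treatment, so 30% is also tried). Control-arm ED use by literacy 50% vs 32% (moderate) or 55% vs 27% (strong); both pairs average 41%. The planned risk ratio 0.23/0.41 = 0.56 is applied in both literacy groups.

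**Step 1: the plan's own figure.** The two-proportion formula with continuity correction, two-sided 0.05 and 80% power gives:
- 41% vs 20%: 84 per group (stated 84)
- 41% vs 25%: 147 per group (stated 147)
- 41% vs 23%: 116 per group (stated 115)

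The sample size therefore reproduces, with the stated 23% effect size read as an intervention rate of 23%, a difference of 41 - 23 = 18 points.

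**Step 2: chance imbalance under simple randomisation.** The SD of the difference in low-literacy share is sqrt(2 x 0.5 x 0.5/115) = 0.066. Then P(|difference| >= 0.10) = 2 x [1 - Phi(0.10/0.066)] = 0.13. With a 30% share it is 0.10.

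**Step 3: what a 10-point imbalance does to the estimate.**
- Using the control-arm gradient: 0.10 x (50 - 32) = 1.8 points; 0.10 x (55 - 27) = 2.8 points.
- Splitting the imbalance evenly over both arms, with the gradient shrunk by the risk ratio in the intervention arm: 1.8 x (1 + 0.56)/2 = 1.4 points; 2.8 x (1 + 0.56)/2 = 2.2 points.

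The standard error of the difference is sqrt[(0.41 x 0.59 + 0.23 x 0.77)/115] = 0.060, or 6 points. The evenly split shift is thus about a quarter to a third of a standard error (1.4/6 = 0.23; 2.2/6 = 0.37), and the larger version is just under half (2.8/6 = 0.47).

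**Step 4: variance explained in the control arm.** R-squared = 0.25 x 0.18^2/(0.41 x 0.59) = 3.3% (moderate) and 0.25 x 0.28^2/(0.41 x 0.59) = 8.1% (strong).

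**Step 5: power.** Simulation, 60,000 trials per setting, 115 per group, 41% vs 23%. The unadjusted chi-squared test is compared with a Mantel-Haenszel test stratified by literacy.

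| Literacy gradient | Simple randomisation: unadjusted | Simple: adjusted | Stratified allocation: unadjusted | Stratified: adjusted |
|---|---|---|---|---|
| 50% vs 32% | 84.1% | 84.6% | 85.0% | 84.9% |
| 55% vs 27% | 84.3% | 85.8% | 85.7% | 86.1% |
| none | 84.2% | 83.7% | - | - |

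Adjustment alone gains 84.6 - 84.1 = 0.5 point and 85.8 - 84.3 = 1.5 points. If literacy is unrelated to ED use it costs 84.2 - 83.7 = 0.5 point. A separate simulation with odds ratios of 1.5, 2 and 3 for low literacy, at 30% and 50% prevalence, agrees: adjustment plus balanced allocation gains about 0 to 2 points.

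**Step 6: type I error.** Under simple randomisation the unadjusted test runs at 5.1-5.2%. With allocation stratified by literacy but the test left unadjusted, it falls to 4.7% (moderate) and 4.4% (strong). The stratified test stays at 4.9-5.0%.

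**The case against.** The strongest reply is that the planned analysis is not wrong. After randomisation an unadjusted chi-squared test controls the type I error with chance imbalance already counted, and Step 6 confirms it. That stands. A reader might infer that an imbalance in literacy would bias the primary result; it would not, because this is sampling variation that the test allows for.

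A reader might also infer that allocation is unstratified, or that literacy has been left out of the model. The protocol supports neither. On allocation it is silent, and such detail may sit in a document not seen here. The covariate list is illustrative and open, so it neither includes nor excludes literacy. What the text does fix is the unadjusted primary test.

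Nor can literacy be called a strong predictor on this evidence. The Background gives a direction and no figure, and it speaks of care for non-urgent conditions, whereas the primary outcome is any ED use. The gradients above are assumptions, and even they explain only 3-8% of control-arm variance. In the moderate case the gain equals the loss incurred if literacy does not matter.

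Finally, the simulation used a Mantel-Haenszel test with two literacy levels. A logistic model with a continuous score and child's age was not simulated, so the power figures indicate the size of the gain and are not exact for that model.

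What survives is that the variable is already collected, it is known before assignment, and it is central to the trial's reasoning. Using it requires only a change to a method the protocol states.

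**Conclusion.** The point holds as a modest improvement in efficiency and credibility. It is not a defect of validity. The primary test is sound, and 115 per group stands, with about 84% power for 41% vs 23% by the uncorrected test.

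Under the assumed 50% low-literacy share and the two assumed gradients, there is a 13% chance of an imbalance of 10 points or more, worth roughly 1.4 to 2.8 points of the planned 18. That could tip a borderline result but not a clear one. Adjustment is worth about 0.5 to 1.5 points of power. With a weaker gradient the gain approaches zero, and with none it becomes a loss of about 0.5 point.

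**What to change.** In section 3(d), make the primary analysis a comparison adjusted for baseline literacy: a logistic model with Group, literacy score and child's age at enrolment, reported as a standardised risk difference with 95% CI. Keep the unadjusted chi-squared test as a supporting analysis. The risk difference keeps the result on the scale used for planning. An odds ratio would read (0.23/0.77)/(0.41/0.59) = 0.43 for a risk that falls by 1 - 0.23/0.41 = 44%.

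In section 3(b), state whether allocation is stratified. If the list is still open, stratify it by literacy level in permuted blocks and keep the adjustment, because balancing without adjusting makes the test slightly conservative.

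The adjustment needs no new data or subjects; its cost is about 0.5 point of power if literacy is unrelated to ED use. Stratification additionally needs a literacy cut-off, which the protocol does not give, and scoring of the test before assignment.

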As a part of the regular standard of care at Danis Pediatrics, at all routine well-child exams, caregivers receive anticipatory guidance, as well as information related to their child's growth and development in the form of Bright Futures handouts. Bright Futures is a series of informative, age-specific, handouts produced by the American Academy of Pediatrics (AAP) for use by providers as a tool to educate patients on growth, development, and safety. All subjects will receive a condensed version of the Bright Futures content at their scheduled 1, 2, 4, and 6 month well child exams. This enhanced standard of care document (ESoC) is designed to be more readable, digestible, and more directly address the most common causes of non-urgent ED visits, than the Bright Futures handouts received as a part of the regular discharge process at Danis Pediatrics.

Following enrollment and assignment into one of the two experimental groups, subjects assigned to the text messaging intervention group will receive four educational messages per week until their child is 6 months of age. Subjects will receive no more than 104 messages during the study period. The text messages directly reflect the Bright Futures and ESoC content, addressing infant development, safety, care, and the most

common causes of non-urgent visits in the first year. Again, all participants will receive ESoC documents from the research team at scheduled 1, 2, 4, and 6 month well child exams.

Upon completion of text messaging and distribution of ESoC handouts, the research team will review the child's electronic medical record, documenting the volume and type of health care utilization until the child is one year old. The research team will type and count visits to the emergency department and Danis Pediatrics, as well as call volume.

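### Section 3d stratifies the treatment effect by self-reported use of the texts, which is measured after randomisation and has no meaning for controls

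*Protocol*

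**What the plan says.** The primary analysis, in Protocol section 3d, is by assigned group: 6-month ED use (no or yes) "will be compared between study groups, Intervention vs. Control, using the chi-squared test of association". Logistic models with Group plus covariates such as age, race and gender follow.

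The next paragraph of 3d turns to checks that messages were delivered and read. The vendor's daily reports show "whether or not a message has been successfully sent to a subject". For reading, the protocol relies on post-test questions about message use and involvement. Of these it says: "These questions will serve as a statistical covariates in the analysis". The stated purpose is to report the effect by level of use: "such that the treatment effect would be stratified by the levels of self-reported use of and involvement with the texts".

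Section 3b fixes who can have used a text. On the control arm it says that "participants will be randomly assigned to either the group that receives only enhanced standard of care documents"; the other arm gets the same handouts plus the texts. On the texts themselves it says that "subjects assigned to the text messaging intervention group will receive four educational messages per week until their child is 6 months of age". The protocol does not say whether controls take the post-test or what value they would be given for text use.

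**The concern.** A treatment effect within a stratum needs treated and control caregivers of the same kind in that stratum. Text use cannot supply this. It is observed only after assignment, and it exists only in the arm that is sent texts. Nothing in the protocol identifies the controls who would have read the texts had they been sent.

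Caregivers who read health messages may have a different ED risk from those who do not, whatever their arm. A use-stratified result can then show benefit in one use group and harm in the other when texting does nothing. Since the same paragraph says the study rests on texts being delivered and read, such a result could be taken as evidence that the texts work when read. It would stand beside a valid primary test and could be given the same weight.

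**Working it through.** **The plan's own figure.** Inputs from section 3d: control risk 41%, Intervention risk 20–25%, two-sided alpha 0.05, power 80%. The phrase about a 23% effect size is read as a 23% Intervention-arm rate. With d the risk difference and p̄ the mean risk:

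n = [1.96·√(2p̄(1−p̄)) + 0.842·√(p₁(1−p₁)+p₂(1−p₂))]² / d², then with continuity correction n′ = (n/4)·[1+√(1+4/(nd))]².

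| p₂ | n | n′ | Protocol |
|---|---|---|---|
| 20% | 74.3 | 83.5 | 84 |
| 23% | 104.2 | 115.1 | 115 |
| 25% | 134.4 | 146.6 | 147 |

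The sample size reproduces. It concerns the as-randomised comparison, so the point below does not touch it.

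**Structure (no assumed figure needed).** There are three ways to carry out the stratification:

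1. *Controls left without a value.* The analysable set is Intervention caregivers only, and Group is constant. The design matrix (intercept, Group, use) has rank 2 of 3, so no treatment effect can be estimated.
2. *Each use level set against all controls.* The contrast can be computed, but it compares self-selected caregivers with an unselected group.
3. *Controls coded as zero use.* With a yes/no use variable, the Group coefficient is exactly the log odds ratio of texted non-users against all controls; a fitted logistic model gave 0.5528 (SE 0.3428) both ways. With three non-zero use levels as indicators, Group equals their sum (rank 4 of 5), and only the contrasts in item 2 remain. With a numeric score, the Group coefficient is an extrapolation to zero use.

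**Size under no text effect.** From the protocol: 41% control risk and 115 per group. Assumed: the share of users and their underlying ED risk, chosen so that the Intervention arm still averages 41%; for example 0.6×35% + 0.4×50% = 41%.

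Worked case, 60% users (69 users, 46 non-users), risks 35% and 50%:

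- Users vs controls: log OR = ln(0.35/0.65) − ln(0.41/0.59) = −0.255. SE = √[1/(69·0.35·0.65) + 1/(115·0.41·0.59)] = 0.316. The ratio is −0.81, giving a rejection probability of about 12.7%.
- Non-users vs controls (the Group coefficient in item 3): log OR = 0 − ln(0.41/0.59) = 0.364, SE = 0.351. The ratio is 1.04, giving about 18.0%.

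Simulation (400,000 trials, number of users binomial) gave these rejection rates:

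| Share of users | Risk, users / non-users | Difference from controls, points | Chi-squared, as randomised | Users vs controls | Group coefficient, controls = 0 |
|---|---|---|---|---|---|
| 60% | 41 / 41 | 0 / 0 | 5.2% | 5.0% | 4.8% |
| 60% | 38 / 45.5 | −3 / +4.5 | 5.2% | 6.7% | 8.2% |
| 60% | 35 / 50 | −6 / +9 | 5.3% | 12.4% | 18.1% |
| 60% | 30 / 57.5 | −11 / +16.5 | 5.1% | 31.6% | 47.3% |
| 40% | 32 / 47 | −9 / +6 | 5.1% | 17.4% | 12.4% |
| 80% | 38 / 53 | −3 / +12 | 5.2% | 7.1% | 17.7% |

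**Selection in the other direction.** If users have the higher risk (60% users, 47% against 32%), rejection is similar at 12.5% and 17.4%, but users now appear harmed.

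**A real effect acting only through use.** Suppose 60% use the texts and their risk falls from 41% to 11%, so the arm averages 0.6×11% + 0.4×41% = 23%. The primary test rejects 84.2% of the time and users vs controls 99.7%. The Group coefficient with controls coded zero has an odds ratio of 1.00 and rejects 4.9%. This masking is specific to that coding.

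**The case against.** The strongest defence is context. The protocol introduces these questions as a validity check on exposure. The primary comparison is stated first and separately, with no covariates. No alpha or decision role is attached to the stratified result, and the covariates named for the logistic models are age, race and gender; entry of the post-test items into those models is not stated. How controls are coded is a detail commonly left to a SAP, and non-estimability arises only if controls are left missing. The Group-coefficient figures need a yes/no use variable. Every use share and risk gap is assumed, the largest row needs a 27.5-point gap between users and non-users, and the bias could run either way.

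Most of this stands as a limit on scope and size. The fault is confined to the use-stratified analysis and to any model that takes in this covariate. The covariate sentence says only that it enters the analysis, so its use in the logistic models is possible but not fixed. The simulated figures illustrate and do not establish the fault.

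The defence does not remove the core problem. The text does not describe use within the Intervention arm; it says the treatment effect itself will be stratified. No coding of controls makes that a randomised comparison, and the protocol names no method that would form comparable control strata.

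**Conclusion.** The concern holds, and the sentence should be changed. As written, section 3d instructs an analysis that either has no estimable treatment effect or compares self-selected caregivers with all controls. That conclusion follows from the design alone.

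The size rests on assumed use shares and selection. With 60% users and no text effect, rejection at a nominal 5% runs from about 7–8% at a 7.5-point risk gap to about 32–47% at a 27.5-point gap. It is 5% if there is no selection, and the sign of the bias is unknown. The primary chi-squared test stays near 5% throughout, and the sample size is unaffected.

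**What to change.** In section 3d, delete the instruction to use post-test text use and involvement as covariates or stratifiers of the treatment effect. State that the effect is estimated by assigned group and that the logistic models take baseline covariates only. Report text use and involvement against ED visits within the Intervention arm, labelled descriptive.

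This costs one sentence, with no new data and no change to the primary test or sample size.

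Optionally, if the effect of reading the texts is wanted, add a complier-average estimate with randomisation as the instrument and self-reported use as the exposure. It needs a rule turning levels of use into an exposure, a plan for post-test non-response, and two stated assumptions: texts have no effect unless used, and self-report is accurate. The delivery reports cannot be the exposure, because they show sending and not reading. The price is precision. Treating the use share as known, the 95% half-width is 1.96·√(0.41·0.59/115 + 0.23·0.77/115) / share = 0.118 / share. That is about 12 points for the as-randomised difference, against about 15, 20 and 30 points at an assumed 80%, 60% and 40% use.
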